6.3 Analysis of AAGA event proportion

Brice questionnaire and Suspected AAGA follow up responses will be analysed to determine the incidence of suspected AAGA in patients undergoing GA for obstetric indication surgery. An expert panel consisting of a minimum of four assessors – including consultant anaesthetists, DREAMY

study representatives and project board members for NAP5 – will independently evaluate all the responses from patients with possible intraoperative awareness. AAGA events will be graded by consensus opinion in accordance with the Michigan Awareness Classification Instrument [Mashour 2010]. Categorisation for impact on the patient will be in accordance with the NAP5 methodology [NAP5], using the same modified NPSA tool to determine severity of psychological impact. Denominator data, based upon the total number of eligible participants enrolled in the study, will be used to calculate a AAGA event proportion for all recruited patients. Site recruitment logs, detailing numbers of excluded patients or patients that declined to participate, will also be used to provide estimates of how representative this is for all obstetric patients undergoing general anaesthesia. Subgroup analysis for emergency LSCS and other surgical procedures will be performed to determine respective event proportions. Agreement between “Brice positive” classification (based upon Brice questionnaire responses alone) and AAGA classification following full review of the Suspected AAGA follow up responses will be declared.

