9.3 Suspected AAGA follow up protocol

Any patient with Brice questionnaire responses indicating possible memories during the anaesthetic episode will be provided with a secondary structured interview schedule/questionnaire to further detail the characteristics and psychological response to their experience (based upon questions in [Appendix 4](#)).

All suspected AAGA cases should be discussed with the local PI or CI. The local investigator or PI should upload the modified Brice CRF responses to the DREAMY REDCap Server as a matter of urgency (ideally on the same day as reported). An explanation of the subsequent DREAMY follow up procedures should be offered to the participant, alongside a choice of initial telephone/face-to-face structured interview schedule or paper questionnaire. The Local Investigator should notify the CI and/or DREAMY Research Team that they have identified a participant with suspected AAGA.

If the participant chooses a paper questionnaire, then this will be administered by the Local Investigator team whilst the participant is still in hospital. Responses are to be transferred according to arrangements with the DREAMY Research Team (to be couriered, collected by a member of the team or transmitted using secure NHS.net email).

If the participant chooses a structured interview schedule, then this can be conducted via telephone or face-to-face. Suspected AAGA interviews will be led by the CI or DREAMY Research Team at the earliest available opportunity. Any travel expenses incurred will be reimbursed to participants.

All Suspected AAGA structured interview schedules and questionnaires are adapted from those used in BAG-RECALL trial [Avidan 2011]) and feature categorical and free-text responses on the detail and nature of recalled events and experiences during anaesthesia, alongside self-reported perioperative context and post-operative psychological consequences.

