12.1.2 Secondary endpoints

The secondary endpoints are:

1. Descriptors of anaesthetic, surgical and patient factors associated with AAGA
2. 3, 6, 9 and 12 month results of the Post-Traumatic Stress Disorder Checklist (PCL-5), for patients with confirmed AAGA. This will be compared with PTSD incidence in the initial cohort of non-AAGA participants.
3. Qualitative description of the experience of AAGA undergone by obstetric patients.

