C. Do you think your awareness experience took place in the operating room or in the intensive care unit or both? Why do you think this?

Operating room During the surgery

D. How long do you think the awareness experience lasted?

Part 4. Do memories of the event still trouble you now?

A. Do you sometimes feel that you are reliving the experience, or that it is happening to you again?

B. Do you have dreams or nightmares about the experience?

C. Do you feel anxious or fearful about something that you were not anxious about before?

D. Do you feel unusually upset or emotionally numb?

E. Have you felt any negative emotions because of your memories?

Fear Helplessness

Anger Frustration

Other (Free Text):

F. Do you avoid any situations as a result of your experiences?

G. Have your social life or relationships been affected?

H. Do you have problems sleeping? Have these changed since your experience?

I. Have you spoken to a health counsellor, GP, psychologist or other professional about these experiences?

Part 4. How would you feel about having an anaesthetic in the future?

A. Would you like to speak to a professional about your experiences?

B. Is it all right with you if we contact you again to talk to you about your experiences?

Yes, you may contact me again

No, I would prefer NOT to be contacted

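### The panel classifies AAGA with the interview's symptom answers in view, so confirmation may be influenced by early distress and PTSD frequency in confirmed cases could be overstated

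*Protocol*

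**What the plan says.** **Who decides, and on what.** Protocol section 6.3 sets up a panel of at least four assessors who "will independently evaluate all the responses from patients with possible intraoperative awareness". The criterion is named: "AAGA events will be graded by consensus opinion in accordance with the Michigan Awareness Classification Instrument". Impact on the patient is a separate categorisation in the same section, "using the same modified NPSA tool to determine severity of psychological impact". Section 6.3 also promises that agreement between Brice-positive status and the "AAGA classification following full review of the Suspected AAGA follow up responses will be declared".

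**What the responses contain.** Section 9.3 describes the Suspected AAGA interview as covering the recalled events, "alongside self-reported perioperative context and post-operative psychological consequences". In Appendix 4, the first of two sections numbered Part 4 includes "Do you sometimes feel that you are reliving the experience, or that it is happening to you again" and "Do you have dreams or nightmares about the experience", together with items on numbness, negative emotions, avoidance, relationships and sleep.

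**Where the classification is used.** Secondary endpoint 2 (section 12.1.2) is the PCL-5 result at 3, 6, 9 and 12 months "for patients with confirmed AAGA", compared with the initial non-AAGA cohort. PCL-5 itself is offered more widely, to every suspected (Brice-positive) woman (sections 6.2 and 9.3).

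The protocol does not state that Part 4 is withheld during classification, that the event is graded before impact, or when the panel sits relative to PCL-5 collection.

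**The concern.** Panel membership of the case group and the outcome reported for that group are not kept apart. The assessors who decide whether an account is AAGA can see early answers on the symptoms that PCL-5 later measures. If a doubtful account is more readily accepted when the woman also reports nightmares or avoidance, confirmed cases will contain too many symptomatic women. PTSD after AAGA would then look more frequent than it is, and the contrast with non-AAGA women would widen even if awareness had no effect.

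The psychological consequences of AAGA are the study's stated secondary aim, so this contrast matters. The problem also cannot be repaired afterwards: once the assessors have read everything, they cannot give a masked classification.

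**Working it through.** The protocol gives no figure on this point, so there is nothing to reproduce. The check has three steps.

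**1. Do the interview symptoms overlap with the outcome?** Appendix 4 (first Part 4) set against the PCL-5 items in Appendix 5:

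| Appendix 4, Part 4 | PCL-5 item |
|---|---|
| A. Reliving | 3 |
| B. Dreams or nightmares | 2 |
| F. Avoidance | 6, 7 |
| H. Sleep | 20 |

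Items D (numbness) and E (fear, anger) also come close to PCL-5 items 14 and 11. The overlap is real.

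**2. Does classification need those answers?** Section 9.2 tells investigators to concentrate on memories of things that could only have happened in theatre during anaesthesia and surgery. That content sits in the Brice answers and in Appendix 4 Parts 1-3. Part 4 concerns the aftermath and adds nothing that this criterion uses.

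**3. How large could the effect be?** Let s be the share of Brice-positive women with Part 4 symptoms. Let a and b be the probabilities of confirmation with and without symptoms, and k = a/b. Then

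share symptomatic among confirmed = s·a / (s·a + (1 − s)·b) = s·k / (s·k + 1 − s).

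None of s, a or b is in the protocol; all values below are assumptions.

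| k | s = 10% | s = 20% | s = 30% |
|---|---|---|---|
| 1.0 | 10% | 20% | 30% |
| 1.2 | 11.8% | 23.1% | 34.0% |
| 1.5 | 14.3% | 27.3% | 39.1% |
| 2.0 | 18.2% | 33.3% | 46.2% |

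Example: s = 0.2, a = 0.8, b = 0.4 gives 0.16 / (0.16 + 0.32) = 33.3%.

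There is a ceiling. Because a cannot exceed 1, k cannot exceed 1/b. If 90% of symptom-free accounts are confirmed, 20% can rise only to 0.20 / (0.20 + 0.8 × 0.9) = 0.20/0.92 = 21.7%.

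These are shares with Part 4 symptoms, not with a positive PCL-5 months later. Suppose confirmation depends on Part 4 symptoms only, and q1 and q0 are the PCL-5-positive proportions with and without them. The endpoint then moves by (change in symptomatic share) × (q1 − q0). That equals the full change only if the two measures coincide, and is otherwise smaller.

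In numbers of women, section 12.2.2 expects about 15 Brice positives under its middle hypothesis. With s = 20% that is 3 symptomatic and 12 not. At 80% against 40%, 2.4 and 4.8 are confirmed, so 2.4/7.2 = 33%. The whole shift turns on how a handful of accounts are decided. Sampling error is also wide: 3 of 15 has an exact 95% interval of about 4% to 48%. Unlike sampling error, this bias would not shrink with more cases.

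**The case against.** A reader might infer that confirmed AAGA is selected on harm, that the PTSD result is inflated, and that the incidence count follows distress rather than recall. The document does not support any of these as stated.

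- **Harm is not a criterion.** Events are graded with a named awareness instrument, and impact with a different tool. That both are done in one sitting is not stated. This stands and rules out the claim of actual selection. It does not remove the exposure: grading is by consensus opinion, and naming an instrument does not mask its users. In the one obstetric Brice study described in section 4, three of five positives were only possible awareness, so doubtful accounts do occur; five cases cannot show how often.
- **The panel is not shown to see lasting distress.** The interview takes place as early as possible, endpoint 2 starts at 3 months, and PCL-5 is not listed among the panel's material. This stands, and weakens the link for women identified in hospital. The link is closest for those first identified at day 30.
- **An unselected analysis is possible.** PCL-5 is collected in all Brice-positive women, and section 12.2.3 plans prevalence for the whole sample and for subgroups. This stands for the data, but endpoint 2 is written for confirmed cases.
- **The incidence hypotheses concern Brice positivity.** The expected counts and the power statement are framed that way, and section 6.3 bases Brice-positive status on the questionnaire alone. This stands: only the panel-classified AAGA proportion could be touched. Section 9.2 does give final Brice classification to the same panel, so that decision too should be made from the questionnaire answers.
- **Masking is incomplete.** Part 2 records fear, helplessness, pain and paralysis at the time. Section 4 reports moderate to severe harm in 51% of those with pain and/or paralysis against 25% with only auditory or tactile sensations. Recall content and later harm are thus expected to be associated without any bias. This stands; it limits the benefit but leaves Part 4 unnecessary for classification.

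**Conclusion.** The point holds as a risk built into a stated procedure, not as a demonstrated bias. Section 6.3 exposes the classifying panel to symptom answers that overlap with the outcome later reported in the cases it confirms. Confirmation may therefore be influenced by those answers, and if so PTSD frequency in confirmed AAGA would most likely be overstated.

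The size cannot be derived from the protocol. It is nil if symptoms do not sway the panel (k = 1), small if nearly all symptom-free accounts are confirmed anyway, and larger if many doubtful accounts are decided on symptoms. The illustrated range, from 20% unchanged up to 33%, rests wholly on assumed confirmation rates, and carries over to PCL-5 only as far as Part 4 symptoms predict it. Any effect on incidence is confined to the panel-classified AAGA proportion. A change is worth making because it is cheap and cannot be made after the panel has read the full responses.

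**What to change.** In section 6.3, stage the review:

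1. Give assessors the Brice answers and Appendix 4 Parts 1-3 only. Record and lock the individual and consensus AAGA grades, with both sections numbered Part 4 and any PCL-5 results withheld.
2. Then release the withheld material for the psychological impact grading, and state that the AAGA grade is not changed after release.

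In section 12.1.2 or 12.2.3, report PCL-5 for all Brice-positive women beside the panel-confirmed cases. This uses data already collected and shows how far the result depends on the panel's selection.

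Cost: case packs split in two, a sentence or two in section 6.3, and slightly more administration per case. The panel, the data collected and patient care are unchanged. The masking is partial, because distress at the time of the event, recorded in Part 2, is part of the recalled experience and properly stays visible.

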The Brice questionnaire [Brice 1970] has been used as a common standard in awareness research. Although minor variations have been applied [Avidan 2009], all retain the same five questions on recall of any events between induction of anaesthesia and emergence. Importantly, direct and systematic questioning is applied when using Brice questionnaires, which contrast with spontaneously patient reporting of AAGA in NAP5. This difference in methodology may partly account for the apparent divergence between the proportion of AAGA consistently reported in the overall surgical population with Brice questioning (~1:660) versus that by NAP5 (~1:19,000 overall). Although few studies have compared methods of AAGA testing, the Brice questionnaire is known to detect more cases of AAGA than unstructured direct questioning [Mashour 2013, Mashour 2009], and timing/repetition of Brice questioning may also influence the output [Mashour 2013, Sandin 2007, Davidson 2005, Leslie 2007]. These limitations, coupled with the debated gulf between incidence of AAGA established by Brice responses alone versus spontaneously reported incidence, mean that Brice has been regarded by some as not the “gold standard” methodology it is frequently implied to be [Cook 2015]. However, where Brice is uniquely important is as a common tool for comparison and as a screening method to identify a subpopulation that may be at need of further investigation.

Brice questionnaires have been applied only once before in obstetric patients [Paech 2009]. This observation study was primarily designed to investigate difficult airways in obstetric patients receiving a GA, but Brice questionnaires were also offered up to day two following surgery. A total 763 of 1095 obstetric patients were provided Brice questionnaires, of whom five cases were “Brice positive”, yielding an estimate of AAGA incidence of ~1:152. Of these, two were classed as “definite” and three as possible awareness. This preliminary study indicates that Brice positivity may indeed be much higher than it is in the general population. However, the lack of follow up beyond 48 hours, the wide confidence intervals and the fact that AAGA was not the study’s primary outcome make these results somewhat difficult to interpret.

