6.2 Data collection procedures

There are three stages to participant data collection:

1. In hospital: Screening for AAGA with modified Brice questionnaires and collection of baseline anaesthetic episode data
2. After hospital: telephone follow up with repetition of the Brice questions at 30 days after the index GA
3. Conditional follow up, dependent upon Brice response: structured interview schedules for participants reporting Suspected AAGA, extended follow up of AAGA patients after 3 months, identification of PTSD risk factors and PTSD symptom screening for 12 months.

Initial AAGA screening will occur at three time intervals following a participant's index GA: 0-24 hours, 24-48 hours and 30 days. 0-24h and 24-48h follow up will consist of a modified Brice questionnaire [Brice 1970, Avidan 2009], including categorical and free text responses (see [Appendix 2](#) for the modified Brice questions). Day 30 (+/- 5 days) follow up will be conducted via telephone (or via email, at participant request) using the same Brice question format and response options. Data collection following discharge of the patient from the local hospital site will be coordinated and conducted by the DREAMY Research Team, rather than local site investigators. Modification to the above timeline for Brice questionnaire administration will only be made in exceptions when patients are unable to provide responses at the pre-specified time points and in agreement with the local PI/CI.

Any patient with Brice questionnaire responses indicating possible recall of events during the anaesthetic episode (hereafter termed "Brice positive") will be provided with a specific structured interview schedule or questionnaire to further delineate the characteristics and psychological response to their experience (adapted from the BAG-RECALL trial [Avidan 2011]). Further repetitions of the Brice questionnaire will not be required after a participant has been declared "Brice positive". See [section 9.2](#) for further detail on Brice questionnaire response classification.

Suspected AAGA face-to-face or telephone structured interview schedules will be organised and led by the DREAMY Research Team and provided at the earliest available opportunity. See [Appendix 4](#) for the structured follow up questions for patients with Suspected AAGA.

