7.3 Discontinuation/withdrawal of participants

Subjects will be able to withdraw at any time up until they have completed the questionnaires and handed them back to the local study investigators. If after this time they change their mind about their participation, they will need to contact the local investigators who would then either return or confidentially destroy their questionnaire responses and demographic information. Participants may also withdraw from the 30 day follow up process by contacting the DREAMY Research Team.

8 Participant Recruitment process

Participant recruitment at a site will only commence once evidence of the following approval/essential documents are in place:

1. REC approval
2. HRA approval
3. Host site confirmation of capacity and capability

All sites participating in the study will also be asked to provide a copy of the following:

1. Confirmation of participating site R&D approval

All participants who wish to enter the study will be screened and consented by the site Principal Investigator, one of the qualified clinicians involved in the study as Local Investigator or an affiliated Research Nurse.

Participants will be recruited from the study start date. Recruitment will last until 12 months after the first patient is recruited in each site.

Participants should be first recruited during the time period 0-24h following the index GA. Omission of recruitment during 0-24h time window does not exclude patients from eligibility and recruitment can still occur at 24-48h or later. However, such patients will be unable to retrospectively complete the earlier Brice questionnaire(s).

Patients will be approached by anaesthetists (PI and/or Local Investigators) during routine follow up of GA procedures in obstetric patients (between 0-24h and 24-48h following the index GA) and provided with information about the study. Consent for inclusion will be taken prior to questionnaire completion. Consent may be taken by Local Investigators or by designated Research Nurses.

9 Study procedures

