12.1 Endpoints

12.1.1 Primary endpoints

The primary endpoint is the proportion of obstetric GA patients reporting AAGA in the included sample.

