No formal estimate is made for the sample size of the baseline comparator group of non-AAGA patients who will be undergoing PTSD screening at 30 days. A lack of clear evidence regarding PTSD prevalence in patients receiving general anaesthesia for obstetric surgery would make such estimations speculative. Therefore, sample size has been preferentially determined by operational issues and consideration of sample size of studies identified in a previous systematic review of post-natal PTSD [Anderson 2012].

12.2.2 *Primary endpoint analysis*

The proportion of obstetric GA patients reporting AAGA will be expressed using binomial confidence intervals and compared with established values (see above for rectification of sample size).

There are three competing hypotheses. First, that the event proportion of Brice positivity in obstetrics is similar to that of the general population (i.e. ~1:660). If so, then we expect ~4 patients (binomial 95% CI 1 – 10). Second, that our incidence of Brice positivity will be similar to Paech’s already reported incidence (i.e. ~1:152 [Paech 2008]). Then we expect ~15 (95% CI 8 – 25) patients. Third, that the ratio between “Brice positive” and spontaneous reporting as in the general population (i.e. 1:660 vs 1:19,000) is maintained for obstetric patients (i.e. ~1:19). Then we expect 118 patients (95% CI 98 – 141). These figures for each of the three possible outcomes will be compared using Fisher’s exact test or chi-squared testing to yield a definitive answer as to which is the most likely hypothesis of the three.

Because we are administering the Brice questionnaire during 0-24h following the index GA (i.e. as soon as possible after GA recovery), we expect to obscure those cases who may otherwise report spontaneously. In other words, we do not expect by our methods to detect spontaneous reporting as such, as the questions will already have been asked. It is possible that some few patients may telephone in after their discharge to report that they now recall AAGA, perhaps triggered by the study, but even that would not fulfil the criterion for spontaneous reporting. We plan to class any such cases as “triggered reporting” and analyse them separately.

Subgroup analysis of the AAGA proportion will be conducted for type and urgency of surgical procedure (including emergency LSCS), de novo conversion from regional anaesthesia to GA and for GA inductions using propofol vs. thiopental.

12.2.3 *Secondary endpoint analysis*

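### The comparison with ~1:152 sets a proportion counted to day 30 against a benchmark collected only to day two

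*Protocol*

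**What the plan says.** - **Endpoint (Section 12.1.1).** "The primary endpoint is the proportion of obstetric GA patients reporting AAGA in the included sample". No time window and no minimum number of completed screens is attached.
- **Screens (Section 6.2).** "Initial AAGA screening will occur at three time intervals following a participant's index GA: 0-24 hours, 24-48 hours and 30 days". A positive answer at any of the three leads into the suspected-AAGA pathway, so day-30 positives enter the numerator. Section 12.2.2 sets aside only unsolicited telephone reports after discharge, not day-30 questionnaire answers.
- **Denominator (Section 6.3).** "Denominator data, based upon the total number of eligible participants enrolled in the study, will be used to calculate a AAGA event proportion".
- **Incomplete screening (Sections 7.3 and 8).** Women recruited late stay in the study without the screens they missed. On the last screen: "Participants may also withdraw from the 30 day follow up process by contacting the DREAMY Research Team".
- **Benchmark (Section 4).** In the earlier obstetric study "Brice questionnaires were also offered up to day two following surgery". Of 1095 women, 763 received them and five were positive. The same section says that "timing/repetition of Brice questioning may also influence the output" and lists the lack of follow-up beyond 48 hours among that study's limits.
- **Comparison (Section 12.2.2).** For the hypothesis that this benchmark applies: "Then we expect ~15 (95% CI 8 – 25) patients". The three hypotheses are then compared by Fisher's exact or chi-squared test, and the section promises a definitive answer as to which is most likely. No proportion restricted to the first 48 hours is planned.

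**The concern.** The protocol recognises that the number and timing of Brice interviews affect how many cases are found. It then compares a count from three interviews over 30 days with a rate from questioning that ended at day two. Any case first reported at day 30 adds to DREAMY's count and could not have been in the benchmark.

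What is at stake is how the second of the three hypotheses is read. Two populations with the same 48-hour rate could look different, and an excess produced by the longer window could be taken as a higher incidence than in the earlier obstetric study. The choice of denominator matters too, but less.

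**Working it through.** **Inputs.** N = 2250 (Section 12.2.1). Benchmark 5/763, questioned to day two (Section 4). Printed expectation about 15, range 8-25 (Section 12.2.2). The protocol states neither the share *s* of all cases that first report at day 30 nor the share *d* of women lost at day 30. I assume s = 20%, 35% or 50% and d = 0% to 40%, with loss unrelated to being a late reporter.

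**1. The plan's own figures.** 5/763 = 0.655%, or 1 in 152.6. Expected count: 2250/152 = 14.8. Exact (Clopper-Pearson) limits for 15/2250, scaled to counts, are 8.4 to 24.7. The printed figures reproduce.

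**2. Window effect, complete day-30 follow-up.** If the 48-hour rate is exactly 1:152, the mean count to day 30 is 14.8/(1 - s). Exceeding the printed range means 26 or more events, from the binomial with n = 2250.

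| s | Mean events | P(26 or more) |
|---|---|---|
| 0% | 14.8 | 0.5% |
| 20% | 14.8/0.80 = 18.5 | 6% |
| 35% | 14.8/0.65 = 22.8 | 28% |
| 50% | 14.8/0.50 = 29.6 | 77% |

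**3. With losses at day 30.** The mean becomes 14.8/(1 - s) × (1 - s·d).
- s = 20%: 18.5 × 0.98 = 18.1 (d = 10%) down to 18.5 × 0.92 = 17.0 (d = 40%). P(26 or more) is 4.7% to 2.5%.
- s = 50%: 29.6 × 0.95 = 28.1 (d = 10%) down to 29.6 × 0.80 = 23.7 (d = 40%). P(26 or more) is 68% to 34%.

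**4. A formal test.** I read Section 12.2.2 as a two-sided Fisher test at 0.05 of x/2250 against 5/763. It first rejects upward at x = 37. With complete follow-up the chance of 37 or more is 0.01%, 0.4% and 10% for s = 20%, 35% and 50%.

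**5. Denominators side by side.** The benchmark divides by the 763 questioned of 1095, or 70%. DREAMY divides by the roughly 2250 enrolled of 3225 eligible (Section 12.2.1), also 70%. DREAMY's counterpart of the 1095 is therefore its eligible patients, not its enrolled women.

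**6. Effect of missed day-30 screens on the to-day-30 proportion.** Understatement = s × d: 0.2 × 0.1 = 2% to 0.5 × 0.4 = 20%.

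**The case against.** The strongest defence is that the day-30 screen deliberately remedies the benchmark's short follow-up, which Section 4 names as a limitation. Only one of three benchmarks is affected. The power calculation rests on 1:660, for which the protocol gives no window, and the 1:19 hypothesis (118 events) is too far away to be confused with 1:152. The late-report shares are assumed, and the named test has little chance of rejecting. All of this stands. It limits the consequence but does not make the two windows comparable.

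Four stronger readings are tempting and are not supported:

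- **That a sizeable group of unquestioned women is counted as negative.** The protocol does not say so. Consent and the first screen belong to one 0-24 h step (Section 6.2), and women unable to complete the questionnaire are excluded (Section 7.2). Few enrolled women are likely to have no screen at all. The realistic gap is a missed day-30 screen.
- **That a late recruit is an unobserved negative.** Each repetition asks about the same anaesthetic (Appendix 2). A woman first asked at 24-48 h is still asked about the whole event.
- **That the benchmark should be restated as 5/1095 = 1:219 to match DREAMY.** Step 5 shows that this pairs the wrong groups.
- **That the hypothesis would probably be rejected wrongly.** Step 4 shows a chance of at most 10% with complete follow-up, even at a 50% late share. Taking 24 events as the threshold (the binomial 97.5% point is 23) would give 12-87%, but the range the protocol prints ends at 25.

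**Conclusion.** The point holds for the comparison with 1:152. The windows differ, the protocol itself says that this can matter, and no matched figure is planned. Under the assumed late shares of 20-50%, an identical 48-hour rate would produce 1.25 to 2 times the expected count with complete follow-up. The count would exceed the printed range with a chance of 6-77%, or about 2.5-68% with 10-40% lost at day 30. The range is wide because the late share is unknown; with no late reports there is no window effect.

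The harm lies in how the result is interpreted against the printed range, much less in formal rejection. Missed day-30 screens work in the opposite direction, so the protocol does not settle the net size, which is a reason to report the two windows separately. It does not follow that the primary incidence estimate is invalid: the all-enrolled proportion is usable, with an understatement of 2-20% under the same assumptions. This should be corrected, but it does not threaten the study.

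**What to change.** - **Section 12.2.2.** For the comparison with 1:152, count only positives from the 0-24 h and 24-48 h questionnaires, over women who completed at least one of those two.
- **Section 6.3.** Beside the all-enrolled figure, report the proportion to day 30 among women with at least one completed Brice questionnaire. Add a sensitivity analysis for women who missed day 30.
- **An estimator to avoid.** A cumulative proportion formed as 1 minus the product of (1 - positives/questioned) over the three screens is not suitable here. If every case is reportable when first asked, and a share f of women is first asked at 24-48 h, the first interval gives p and the second about f·p. The product form then gives about (1 + f)p, which is 1.10 to 1.30 times the truth for f = 10-30% (assumed). Section 8 expressly permits such late recruitment.

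The cost is wording in two sections, one additional proportion and a slightly smaller denominator, hence a slightly wider interval. The repetitions are already scheduled separately (Section 10.2), so no new data are needed.
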